##### *Study procedures*

##### Assessment:

The subject's cognitive and physical function will be assessed at the start of the study. Some assessments may be audio-recorded for scoring and reliability assessment.

Cognitive Assessment:

- a) Reading Span (RSPAN) and Operation Span (OSPA): assesses working memory capacity. These two tests will allow us to categorize subjects into high vs low working memory, which will allow us investigate how acute exercise effects vary as a function of individual differences in baseline working memory ability (Objective 3b).
- b) Digit Span: assesses the central executive component of working memory
- c) Verbal fluency (semantic and letter): assesses the verbal component of executive function
- d) Color-word Interference Test: assesses the inhibition component of executive function
- e) Hopkins Verbal Learning Test: assesses verbal learning and memory (immediate recall, delayed recall, delayed recognition)
- f) Brief Visuospatial Memory Test- Revised: assesses visuospatial memory (immediate recall, delayed recall, delayed recognition)
- g) Digit Symbol Substitution: sensitive to the effect of brain damage, dementia, age and depression on task completion
- h) American National Adult Reading Test- Revised: estimates intelligence in based on reading of words with irregular grapheme-to-phoneme conversion.
- i) Edinburgh Handedness Inventory: assesses handedness
- j) *Task practice:* Subjects will be administered a practice word learning task at baseline to familiarize them with the novel word learning paradigm.
- k) Discourse production: Subjects will be asked to answer two open-ended questions in order to get a measure of their connected speech.

The following measures will be administered to participants with aphasia:

- a) Comprehensive Aphasia Test- assesses general language ability
- b) Philadelphia Naming Test- assesses confrontation naming ability
- c) Pyramids and Palm Trees- assesses semantic processing ability

Physical Assessment:

Submaximal Treadmill Exercise Test (participants not on beta blockers): The YMCA test, which estimates maximal volume oxygen uptake (VO2max) using an “extrapolation” method, will be administered. This test will provide an indication of aerobic capacity and will be used to set subjects’ individual target training zone for exercise training. Heart rate monitors will be used to ensure subjects are maintaining their target heart rate and to prevent heart rate increases above levels that are considered safe.

Maximal Treadmill Exercise Test (participants on beta blockers). Participants will undergo maximal treadmill exercise until exhaustion using the modified Balke protocol

to determine peak oxygen uptake (VO2 max). The protocol consists of a series of 3-minute stages in which speed and incline are increased in a stepwise manner. Levels of mixed expired oxygen, carbon dioxide, and ventilation are recorded at rest and every 30 seconds during exercise using a breathing apparatus with metabolic cart (Sensormedics). The VO2 max is defined as the highest VO2 rate observed during maximal exercise. A registered nurse (RN) will be present for the entire test and manually monitor blood pressure at baseline and during each stage of exercise, as well as monitor continuous EKG recordings. This same protocol is being used by Co-I [name] in other exercise-based studies that involve older adults.

Word learning paradigm:

A Dell laptop computer running EPrime 2.0 software and paired with a response box will be used to standardize stimuli presentation in the learning task and record the speed and accuracy of responses to the word recall and recognition tasks. Familiar objects will be paired with two-syllable nonwords that are 5-6 letters in length and phonologically plausible in the English language. Sets of stimuli will be balanced on the frequency and familiarity. The order of stimuli sets will be counterbalanced across subjects and conditions. During the word learning task, familiar objects will be randomly presented along with the target nonword, which will also be heard through headphones. Following the learning task, subjects will be administered a recognition task and a cued recall task. Verbal responses will be audio-recorded for scoring and reliability assessment. The number of stimuli, duration and number of exposures to stimuli, and feedback during testing will be manipulated to identify the optimal learning paradigm for investigation of acute exercise effects on word recall (Objective 1).

Exercise/Stretching:

- a) Exercise: Subjects will engage in supervised moderate-intensity cycling for 30 minutes with a warm-up and cool-down. They will be asked to reach and maintain their individual physiological training target (i.e., heart rate at which 50-75% of maximal oxygen uptake would be achieved as predicted by sub-maximal test administered during the baseline assessment).
- b) Stretching: Participants will participate in an upper- and lower-extremity stretching program for 30 minutes. The stretching program will provide the opportunity for 30 minutes of interaction without increasing heart rate.

Exercise and/or stretching will be paired with a novel word learning paradigm to determine the effect of moderate-intensity aerobic exercise (compared to a stretching control) on word recall (Objective 2). The exercise/stretching will be administered before and/or after word learning to better understand how acute exercise effects vary as a function of timing (Objective 3a).

Subjects will be asked to avoid any exercise that is not part of the study on training days and to avoid exercise before testing on the testing only days. No other restrictions will be placed on subjects regarding their exercise routines.

Mood and arousal measures:

Bond and Lader's Mood Rating Scale will be administered to assess the effect of moderate-intensity exercise and gentle stretching on mood and arousal. Ratings will be obtained prior to the second word recall and recognition test in each session. As heart rate is physiological marker of arousal, we will also take heart rate measurements after subjects complete of the rating scale. These data will be used in secondary analyses to investigate the relationship between mood and arousal and performance on the recall and recognition tests.

Post-session and post-study questionnaires:

Post-session questionnaires will be used to explore how subjects feel physically and psychologically after a session. A rating scale to measure current level of motivation to learn novel words, current stress level, perceived difficulty of learning the words, and quality of the previous night's sleep will also be administered at each session. The post-study questionnaire will be used to explore the subject's perception of difficulty of the experimental conditions and any expectations regarding ease of learning.

Daily Diary:

To monitor exercise and sleep during the experimental conditions, subjects will be asked to keep a daily diary of any exercise outside of the training sessions (type, intensity, duration) as well as the amount of sleep.

Blood draws:

To explore the neurophysiological correlates of exercise-enhanced word learning (Objective 4), fasting whole blood will be collected from some subjects during a baseline blood draw and during subsequent training conditions. Samples will be collected by a certified phlebotomist, via venipuncture or peripheral venous line into pre-cooled plasma EDTA tubes and serum separator tubes (~40 ml per visit). The time line for collection of blood samples is as follows:

*Baseline:* every 15 minutes for one hour to demonstrate reliability.

*Experimental:* Immediately prior to exercise and stretching, immediately post exercise and stretching, immediately post word learning, and 15 minutes post word learning. The blood draws will occur on two days during the training conditions.

Following collection, tubes will be transferred in sealed biohazard bags. Plasma volume will be measured as described by Dill and Costill (1974). Lactate will be measured by an Accusport Lactate Analyzer (Roche Molecular Biochemicals, Mannheim, Germany).

## 7. Patient Evaluation and Data Collection Timeline

Study Visit	Activity			# of hours
Pre Training				
Assessment I	· Consenting			2
	· Screening Tests			
	· Study Tests			
Assessment II + Blood draw (if applicable)	· Study Tests			2
	· Blood sample taken every 15 minutes for 1 hour			
Assessment III	· Study Tests			2
Training Conditions (in random order)				
Exercise + Word Learning + Blood draw** (if applicable)	M	W	F	**Before exercise, after exercise, after word learning, 15 min after word learning
	test/train/test	test/train/test	test/train/test	
			test	
	One week break			
Stretching + Word Learning + Blood draw** (if applicable)	M	W	F	**Before stretching, after stretching, after word learning, 15 min after word learning
	test/train/test	test/train/test	test/train/test	
			test	
	One week break			

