**Methods:** We will compare word learning in up to four conditions using a within-subjects crossover design. Individuals aged 65-89 years (healthy older adults and MCI) and 35-89 years (individuals with aphasia) who meet the eligibility criteria will be offered enrollment. In the exercise conditions, participants will engage in 30 minutes of moderate-intensity cycling (with a warm-up/cool-down) before or after word learning. In the stretching conditions, participants will engage in upper- and lower-limb stretching for 30 minutes before or after word learning. In the word learning task, participants will be asked to learn novel words ("flark") for a familiar object ("cup") and will engage in tests of recall and recognition. Each condition will last two weeks. In week 1, training /testing will take place on Monday, Wednesday and Friday of week 1 to measure immediate retention. In week 2, testing will take place on Friday to measure one-week retention. To measure serum levels of BDNF and dopamine, blood samples will be taken at baseline (every 15 minutes for one hour) and in the two training conditions when exercise/stretching occurs before word learning (immediately before exercise/stretching, immediately after exercise/stretching, immediately after word learning, and 15 minutes after word learning).

**Clinical Relevance:** The aging population of the US is expected to more than double by 2060, and a similar trajectory is expected within our aging veteran population.

Additionally, stroke affects 795,000 individuals per year, and up to 30% are left with chronic disability including language impairment. MCI can also have an impact across all cognitive domains, including language and memory (Arnaiz & Almkvist, 2003). The declines in communicative function that are present in healthy older adults and those with aphasia often result in reduced independence and psychosocial well-being, and they may contribute to poorer health outcomes. Investigating an exercise-based approach to improving word retrieval is clinically relevant and has the potential to have a significant impact on the functioning and well-being of thousands of aging veterans.

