## 8. Participant Selection

The study will enroll up to 100 healthy older adults and up to 50 older adults with MCI and stroke-induced aphasia.

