Official Study Title:

Acute Exercise Effects on Word Learning in Aging and Stroke-induced Aphasia

NCT# 03370471

Document Date: 09/16/19

Statistical Analysis Plan

The following analyses apply to data from healthy adult participants who completed the study:

Primary Outcome

Aim 1. We will use a mixed effects model approach to fit repeated measures ANOVAs to word recall scores obtained at three time points: 1) after learning (acquisition), 2) immediately before exercise or stretching on two days (consolidation), and one week after the final learning session (long-term recall).

Secondary Outcome

Aim 2. We will use a mixed effects model approach to fit repeated measures ANOVA to serum BDNF concentration levels (pg/mL) obtained at four time points: 1) before exercise or stretching, 2) immediately after exercise or stretching, 3) immediately after learning, and 4) 15 minutes after learning.

Post-hoc Analysis:

We will use a mixed effects model approach to fit repeated measures ANOVAs to word recognition scores obtained at three time points: 1) after learning (acquisition), 2) immediately before exercise or stretching on two days (consolidation), and one week after the final learning session (long-term recall).

The following analyses apply to data from participants with aphasia who completed the study:

Primary Outcome

Aim 1. We will calculate gains for word recall at three time points: 1) after learning (acquisition), 2) immediately before exercise or stretching on two days (consolidation), and one week after the final learning session (long-term recall).

Secondary Outcome

Aim 2. We calculate means of serum BDNF concentration level (pg/mL) obtained at four time points: 1) before exercise or stretching, 2) immediately after exercise or stretching, 3) immediately after learning, and 4) 15 minutes after learning.

Post-hoc Analysis:

We will calculate gain scores at three time points: 1) after learning (acquisition), 2) immediately before exercise or stretching on two days (consolidation), and one week after the final learning session (long-term recall).

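### The protocol does not specify a balanced exercise/stretching order, and the aphasia analysis has no step that would remove the effect of a chance imbalance

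*Protocol*

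**What the plan says.** The Methods part of the protocol abstract sets out the design: "We will compare word learning in up to four conditions using a within-subjects crossover design". The timeline table in protocol section 7 shows an exercise condition and a stretching condition under the label "Training Conditions (in random order". That label is the only statement on how order is assigned. Neither document gives a sequence ratio, a block scheme, an allocation list or stratification by population.

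Counterbalancing is described once, in the word learning paradigm part of protocol section 6, and it concerns the word lists: "The order of stimuli sets will be counterbalanced across subjects and conditions". The cognitive assessment list in the same section adds a familiarisation step: "Subjects will be administered a practice word learning task at baseline to familiarize them with the novel word learning paradigm".

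On numbers, protocol section 8 gives caps only: "The study will enroll up to 100 healthy older adults" and "up to 50 older adults with MCI and stroke-induced aphasia". The second cap is not divided between MCI and aphasia.

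The primary analysis for aphasia in the SAP reads "We will calculate gains for word recall at three time points", and BDNF is summarised by means. Both are restricted to participants who complete. No model, between-condition test, period term or breakdown by sequence is named. For healthy adults the SAP plans "We will use a mixed effects model approach to fit repeated measures ANOVAs to word recall scores obtained at three time points", without listing the fixed effects. It has no section for MCI.

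**The concern.** In a crossover, each participant learns a second list of nonwords (up to a fourth) after having already learned one. Performance on the later list may be better because the task is familiar, or worse because earlier nonwords interfere. If equal numbers take each condition first, this period effect cancels from the raw exercise-minus-stretching mean. If they do not, part of it stays in.

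Counterbalancing the word sets protects against one list being harder than another. It does not protect against position, because a participant's second condition is second whichever list is used.

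The matter is most exposed in aphasia. The group may be small, so a lopsided split is plausible. The planned output is descriptive, so nothing in it would show or remove the shift. A reader comparing the two conditions' gains could not tell an exercise effect from the residue of an uneven order.

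**Working it through.** The documents give no sample-size calculation, SD, effect size or sequence split, so there is no planned figure to reproduce. The check has four steps.

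**1. Shift in the raw comparison (two conditions).** Let τ be the true exercise-minus-stretching effect and π the change from first to second period. A stretching-first participant exercises in period 2 and has expected difference τ + π. An exercise-first participant has τ − π. With n_S stretching-first, n_E exercise-first and n = n_S + n_E:

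mean difference = τ + π × (n_S − n_E)/n

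For splits with n_S the larger, the share of π passed on is:
- 60:40: 0.6 − 0.4 = 20%
- 70:30: 0.7 − 0.3 = 40%
- 80:20: 0.8 − 0.2 = 60%

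The sign reverses if the imbalance runs the other way.

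**2. Chance of a lopsided split.** Assume simple 1:1 randomisation, so n_S is Binomial(n, 0.5), and count both directions. Example for n = 10, 7:3 or worse: 2 × (120 + 45 + 10 + 1)/1024 = 352/1024 = 34%. The aphasia group size is an assumption. The value 25 corresponds to an equal division of the shared cap of 50, and 50 to aphasia filling it.

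| n (assumed) | 60:40 or worse | 70:30 or worse | Mean absolute share of π passed on |
|---|---|---|---|
| 10 | 75% | 34% | 25% |
| 20 | 50% | 11.5% | 18% |
| 25 | 42% | 4.3% | 16% |
| 50 | 20% | 0.7% | 11% |

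**3. Size of the shift.** The documents do not give π. In units of the SD of the within-person difference, assumed values of 0.2, 0.5 and 0.8 give:
- 7:3 split: 0.4 × π = 0.08, 0.20 and 0.32 SD
- 8:2 split: 0.6 × π = 0.12, 0.30 and 0.48 SD
- 5:5 split: 0 in each case

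**4. What a test would do, if one were run.** The aphasia plan names no test, so this is illustrative. A paired t-test without a period term was simulated with τ = 0, two-sided 0.05 (assumed) and 15,000 runs per setting. The type I error was:
- averaged over all random splits (n = 10 to 50, π = 0.5 or 0.8 SD): 0.047 to 0.050, with the estimate centred on zero
- given a particular split, π = 0.5 SD: 0.061 (n = 10, 7:3), 0.110 (n = 10, 8:2), 0.101 (n = 20, 14:6), 0.071 (n = 50, 30:20)
- given an exactly equal split: about 0.03 at π = 0.5 SD and about 0.015 at 0.8 SD, so the unadjusted test is conservative
- with period adjustment, in every setting run: 0.046 to 0.055

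Period adjustment averages the two sequence means: [(τ + π) + (τ − π)]/2 = τ at any split. It costs precision when the split is uneven. The variance is (σ²/4)(1/n_S + 1/n_E) against σ²/n, a ratio of 1/(4 × 0.7 × 0.3) = 1.19 at 70:30 and 1 at 50:50. Balance in the design and adjustment in the analysis therefore do different jobs.

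**The case against.** Much can be said on the other side.

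- **Random order does not exclude balance.** Blocked randomisation is also random. A reader might infer from the table label that order is known to be unbalanced, but the documents do not say so. What stands is that balance is not specified, although it is for the word sets.
- **The error is not directional.** A reader might infer that practice will be passed off as an exercise benefit. Under random order the shift averages to zero and can hide a benefit as easily as mimic one. It does harm only once a lopsided split has occurred, and the trial is run once.
- **The groups may not be small.** Near the shared cap, a 70:30 split is rare (4.3% at 25, 0.7% at 50). The risk is material at about 20 or fewer, a size that the documents neither state nor rule out.
- **The period effect may be modest.** The baseline practice task may reduce it, though it cannot be assumed to abolish it over several sessions per condition. The reference for the gains is also undefined. Gains taken within a condition would cancel a constant shift between periods. They would not cancel faster learning of a later list, or interference that slows it.
- **MCI has no planned result to distort.** The SAP contains no MCI analysis. That is a separate gap, and the present point rests on aphasia.
- **Balance at randomisation can be lost.** Only completers are analysed, so dropout can undo equal numbers. This is correct, and it is why the fix needs a reporting step as well as an allocation step.

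**Conclusion.** The point holds as a gap in specification with a cheap remedy. Nothing in either document ensures equal numbers starting with exercise and with stretching, and nothing in the aphasia analysis would remove the effect of unequal numbers. The formula for the shift is exact for two conditions; its size in this trial cannot be fixed. It depends on an unstated group size, an unstated period effect and an allocation method that is described only as random. If randomisation is simple and the aphasia group numbers 10 to 20, a split that passes on at least 40% of the period effect has a chance of roughly one in three (34%) to one in nine (11.5%). At 25 or more the chance is below 5%.

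The documents do not support a claim that the trial is biased towards exercise, that its order is in fact unbalanced, or that MCI results are affected. With four conditions there are 4! = 24 possible orders. A small group drawn at random from these would not be assured of balance in position or in which condition follows which.

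**What to change.** In protocol section 7, replace the wording on random order with text such as:

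*Within each population, participants are randomised 1:1 to exercise-first or stretching-first in concealed permuted blocks of varying size. If four conditions are used, participants are randomised in blocks to the four sequences of a Williams square. Stimulus-set order is balanced across sequences as far as numbers allow.*

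The last clause is needed because full crossing of four sequences with even four set orders gives 4 × 4 = 16 cells, which may be more than a small aphasia group can fill.

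In the SAP, for aphasia, add:

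*The number of participants randomised to and completing each sequence will be reported. Exercise and stretching results will be shown by sequence, or as the average of the two sequence-specific differences (period-adjusted).*

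The SAP should also say what the gains are measured from.

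The cost is a new allocation list, one amended protocol passage and a little more analysis. The downside is that the last assignments in a block may be guessed; varying block sizes and concealing the list limit this. If enrolment is too far on to change the allocation, the SAP addition alone removes the shift, at some loss of precision when the split is uneven. If blocked allocation is already in use, stating it closes the allocation half of the point.

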## 8. Participant Selection

The study will enroll up to 100 healthy older adults and up to 50 older adults with MCI and stroke-induced aphasia.

### Recruitment

Individuals will be recruited from the Atlanta VA Rehab R&D Subject Registry (IRB00000159) based on the inclusion and exclusion criteria. The Subject Registry study staff will query the data base of all patients meeting the inclusion and exclusion criteria who have consented to be contacted for research purposes and will print out their contact information. The Principal Investigator or study staff will contact these individuals and summarize the study procedures.

Additionally, participants may be recruited from VA's Information and Computing Infrastructure (VINCI) to enhance recruitment goals within the VISN. Potential Veteran subjects will be mailed an IRB approved recruitment letter, as well as an opt in/opt out response form to be returned using a postage paid envelope. This will allow for potential subjects to indicate whether they would like to be contacted in the future related to the study. If no response is received within two weeks, we will follow up with a phone call to gauge subject interest.

Finally, VA healthcare providers, Emory Alzheimer's Disease Research Center, Emory Rehabilitation Hospital, StrokeNet, other investigators, word of mouth and via advertisements.

Individuals who indicate interest in participating will undergo a phone screen comprised of questions about cognitive and physical function. Those who "pass" the phone screen will be provided a copy of the informed consent and will be scheduled for an orientation session. The PI/Co-PI or their trained study staff will go over and describe the consent in a quiet room. Prior to providing written consent, potential subjects will be given the chance to ask questions and the PI/Co-PI or study staff will ask questions to ensure the potential subject understands what the study entails.

Inclusion criteria:

- age 65-89 years (healthy older adults and individuals with mild cognitive impairment) and 35-89 years (individuals with aphasia)
- English as first and primary language
- "low physical activity" on the International Physical Activity Questionnaire
- *physician's written medical approval for participation in moderate-intensity exercise*

Exclusion criteria:

- any comorbid condition with exercise contraindications
- current use of hormone replacement therapy or dopaminergic drugs
- use of anti-depressant or anti-psychotic drugs for less than 3 months
- current use of illicit drugs
- consumption of >14 standard alcoholic drinks/week
- consumption of > 1 pack of cigarettes/day
- uncorrected hearing or vision impairments that could interfere with study procedures
- < 26 on the Montreal Cognitive Assessment (healthy older adults only)
- low mood or depression as indicated by > 10 on the Beck Depression Inventory

Potential Benefits

Subjects who participate in the study may benefit from an improved awareness of their cardiovascular fitness level and greater confidence in knowledge of their cardiovascular fitness level.

Protection Against Risk

Fatigue, frustration or anxiety during testing will be managed by PI [name] who is an experienced speech-language pathologist with expertise in managing emotional reactions to performance on assessments. Management may include verbal encouragement or short rest breaks, as necessary. In our experience, frustration or anxiety that cannot be managed by study personnel is rare. Additionally, we will decrease testing burden for participants, when possible.

That is, [name] study entitled "Beyond lesion-language mapping in aphasia: A novel imaging-based prediction model" (IRB#104270) and [name] study entitled "Transcranial Direct Current Stimulation (tDCS) as an Adjuvant to Phonemotor Treatment for Aphasia" (IRB#102536) also investigate stroke and aphasia. While the question for this study is different, the framework is in place to use assessment data collected in [name] and [name] study to reduce the number of assessments in this study. Specifically, we may obtain a participant's data on the *Western Aphasia Battery-Revised (WAB-R)*, *Comprehensive Aphasia Test (CAT)*, *Hopkins Verbal Learning Test-Revised (HVLT-R)*, *Brief Visuospatial Memory Test-Revised (BVMT-R)*, *Beck Depression Inventory-II*, and *Boston Naming Test (BNT)*.

Several precautions will be made to reduce the risk of exercise-related injuries:

- Warm-up and cooling down components are included to minimize injuries;
- At each exercise session, subjects will be questioned about the presence of musculoskeletal symptoms;
- Study staff will be instructed to be alert for the emergence of symptoms of angina and shortness of breath;
- Subjects will be instructed to discontinue exercise if there is significant pain, weakness, or joint swelling after exercise;
- We will ensure that the site has immediate access to a phone and that provision of interventions and evaluations are undertaken in the immediate vicinity of a phone. Study staff will be encouraged to carry cell phones during testing and training;
- All testing and training activities will occur inside an air-conditioned facility because environmental extremes are poorly tolerated;
- Subjects will be provided fluids and the opportunity to rest, if necessary.

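### The physician approval required at entry is worded for moderate-intensity exercise only, and nothing extends it to the maximal treadmill test given to participants on beta blockers

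*Protocol*

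**What the plan says.** **Approval at entry.** Protocol section 8, Recruitment, lists among the inclusion criteria "physician's written medical approval for participation in moderate-intensity exercise". The exclusion criteria that follow add "any comorbid condition with exercise contraindications".

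**Baseline exercise tests.** Protocol section 6, Physical Assessment, splits participants by drug use. One paragraph opens "Submaximal Treadmill Exercise Test (participants not on beta blockers" and the next "Maximal Treadmill Exercise Test (participants on beta blockers" (both cut here before the closing bracket). Of the second group it says: "Participants will undergo maximal treadmill exercise until exhaustion using the modified Balke protocol". On supervision of that test it says: "A registered nurse (RN) will be present for the entire test and manually monitor blood pressure". Continuous EKG monitoring is also stated.

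**Study exercise.** Protocol section 6, Exercise/Stretching, says: "Subjects will engage in supervised moderate-intensity cycling for 30 minutes with a warm-up and cool-down". The individual target is the "heart rate at which 50-75% of maximal oxygen uptake would be achieved as predicted by sub-maximal test administered during the baseline assessment".

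**Precautions.** The list under Protection Against Risk in section 8 covers warm-up and cool-down, questions about musculoskeletal symptoms, alertness for angina and breathlessness, access to a phone, indoor conditions, fluids and rest. It mentions neither the maximal test nor medical clearance.

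The SAP does not touch this point.

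**The concern.** The protocol chose a physician's written approval as an entry safeguard and stated the exercise level to which it applies. It then gives one subgroup an exercise exposure above that level. A letter that clears a participant for moderate-intensity exercise, and nothing more, meets the criterion in full, and section 6 then takes that participant to exhaustion if he or she is on a beta blocker.

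What is at stake is participant safety. The people concerned are aged 65-89, or 35-89 if they have aphasia after stroke. All must report low physical activity to be eligible. They are assigned to the harder test because they take a beta blocker.

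A second consequence is analytic. The exercise condition is defined by an individual intensity target, and the route to that target is written only for participants who are not on beta blockers. The comparison of exercise with stretching presupposes that the target is defined for everyone.

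**Working it through.** The plan states no figure on this point, so the check is a side-by-side reading.

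| Element | Participants not on beta blockers | Participants on beta blockers | Protocol source |
|---|---|---|---|
| Approval required at entry | Moderate-intensity exercise | Moderate-intensity exercise | Section 8, inclusion criteria |
| Baseline treadmill test | Sub-maximal | Maximal, to exhaustion | Section 6, Physical Assessment |
| Study cycling | 50-75% of maximal oxygen uptake | 50-75% of maximal oxygen uptake | Section 6, Exercise/Stretching |
| Stated source of training target | Sub-maximal test | Sub-maximal test, which they are not given | Section 6, Exercise/Stretching |

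1. **Does the approval match the intervention?** Yes. Both the criterion and the cycling paragraph use the term moderate intensity.
2. **Does the approval, as worded, match the baseline test for participants on beta blockers?** No. A test to exhaustion goes to the highest uptake the person can reach, whereas the cycling is capped at 75% of the maximum.
3. **Does any other text close the gap?** No section widens the approval for participants on beta blockers, asks for approval of maximal exertion, or excludes these participants.
4. **Is the order fixed?** The timeline in section 7 lists screening tests and study tests over three assessment visits. It places neither the approval nor the treadmill test, so the documents do not say that one precedes the other.
5. **Is the branch carried into training?** No. The sub-maximal paragraph says that its result sets the training zone. The maximal paragraph says that it determines peak uptake but not that it sets the zone. The exercise paragraph names only the sub-maximal test. The measured maximum may be intended as the basis for participants on beta blockers, but this is not written.

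**Size, as an illustration only.** Maximum enrolment is 100 + 50 = 150. The documents give no frequency of beta-blocker use. If it is 10%, 150 × 0.10 = 15 people are affected; if it is 40%, 150 × 0.40 = 60. Both percentages are assumptions, and 150 is a ceiling. The mismatch does not depend on them.

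**The case against.** The strongest reply is that the criterion sets a minimum and is written for the intervention. Only the inclusion criterion speaks about approval; the assessment paragraph is silent on it, so a site can comply with both. That stands. A reader might infer that the two sections contradict each other, but they do not: the approval is narrower than the set of exercise procedures.

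Second, prior screening does exist. The exclusion for exercise contraindications carries no intensity limit and on its face reaches the treadmill tests. This also stands, and a reader should not infer that participants arrive at the maximal test unscreened. But the exclusion names neither an intensity nor an assessor, and the protocol asks for a physician's approval in addition to it.

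Third, the maximal test has the closer supervision. A nurse, blood pressure at baseline and at each stage, and continuous EKG are stated for it and not for the sub-maximal test. The protocol adds that the same procedure is used in other studies involving older adults. Some precautions refer to evaluations and to testing as well as training, and nothing limits those words to the word-learning tests. All of this lowers the risk. It is protection during the test, however, not approval beforehand, and the protocol does not say what clearance those other studies required.

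Fourth, the approval form is not available. It may describe the treadmill test, and an individual physician may clear more than the criterion asks. It would therefore be tempting, but unsupported, to say that participants are in fact tested beyond their written approval or that physicians have no opportunity to object. The documents show only the minimum that the protocol requires.

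**Conclusion.** The point holds as a mismatch of scope with a bearing on participant safety. The required physician approval is worded for moderate-intensity exercise, participants on beta blockers are given a test to exhaustion, and no text states that the approval covers it. The contraindication exclusion, the monitoring and the general precautions reduce the risk but do not replace the approval that the protocol itself made a condition of entry. The mismatch over the source of the training target suggests that the beta-blocker branch was added to the assessment section without being carried through to eligibility or training.

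Its reach is every enrolled participant on a beta blocker, a number that the documents do not give. The conclusion rests on reading the criterion by its plain words and on there being no broader requirement elsewhere in the available text. A broader approval form would reduce the practical consequence but would still leave the protocol needing alignment. Nothing here implies that the maximal test is the wrong test, or that any particular clearance rule is right.

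**What to change.** The sponsor and its clinicians should reconcile three places in the protocol: the inclusion criterion on physician approval (section 8), the two baseline treadmill tests (section 6, Physical Assessment) and the training target (section 6, Exercise/Stretching). After the change, the scope of the required written approval and the exercise tests actually performed should agree, and the source of the training target for participants on beta blockers should be consistent with the test they take. How to achieve this, including which test is used and what clearance is needed, is a clinical decision on which this review takes no view.

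The cost is a wording change to the criterion and the existing approval form, with a matching edit to the training-target sentence. Depending on how the sponsor resolves it, a few participants may not be cleared.
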